3.5.2.3 Follow-up (Visit 4) / Early-Termination Visit

The following procedures will be performed at Visit 4, or if the subject discontinues early, at the early-termination visit:

- Record concomitant medications (see Section 3.4.7.2)
- Measure and record FEV₁
- Record AEs

3.5.3 Procedures for Subjects Who Prematurely Withdraw from the Study

Any subject who discontinues treatment prematurely should have an early-termination visit conducted as soon as possible to complete the assessments indicated in Table 2 and Section 3.5.2.3.

3.5.4 Efficacy Assessment

3.5.4.1 Self-Monitored Blood Glucose

Subjects will measure their blood glucose using the Sponsor-provided blood glucose meter and corresponding supplies (lancets, control solutions, test strips, etc.). Subjects will be instructed at both Visits 2 and 3 to take SMBG values 15 minutes before their AfreZZa dose, immediately before administering their dose of AfreZZa (t=0; baseline), and at 30, 45, 60, 90 and 120 minutes after AfreZZa dosing. Additional SMBG measurements may be taken per Investigator discretion.

3.5.5 Safety Assessments

3.5.5.1 Medical History and Demographics

A detailed medical history should be taken to assess whether or not subjects meet the inclusion/exclusion criteria, including history of diabetes (e.g., age at onset of diabetes, start and stop dates of previous insulin treatments, treatment name, dose[s], frequency and method of dose delivery, date of clinical diagnosis of T1DM or T2DM). In addition, subjects will be queried about drug and environmental allergies, family pulmonary disease history, and any change in their smoking status.

Demographic data, including age (years), race, ethnicity, and gender (male, female, other, or “decline to state”) will also be collected.

3.5.5.2 Physical Examinations

A complete physical examination, including general appearance, ear, nose, throat, lung, and cardiac auscultation will be performed at Visit 1.

Abbreviated physical examinations will be performed as deemed appropriate by the Investigator for safety reasons; these abbreviated physical examinations will include, but are not limited to, general appearance, respiratory and cardiovascular systems, and other evaluations, as needed.

All changes identified as clinically noteworthy must be recorded in an AE page of the CRF.

3.5.5.3 Height and Weight

Height, in centimeters, should be measured when the subject's shoes are off, feet together, and arms by the sides. Heels, buttocks, and upper back should also be in contact with the wall when the measurement is made.

Body weight, in kilograms, should be obtained with the subject wearing undergarments or very light clothing and no shoes, and with an empty bladder. The floor surface on which the scale rests must be hard and should not be carpeted or covered with other soft material. The same scale should be used throughout the study and calibrated on a regular basis as recommended by the manufacturer.

The body mass index (BMI) value will be calculated based on the height and weight.

3.5.5.4 Vital Signs

Vital signs will include body temperature, respiratory rate, pulse, and sitting systolic and diastolic blood pressures. Vital sign measurements will be recorded with the subject in a sitting position for 5 minutes before the measurement is taken.

3.5.5.5 Pulmonary Function Tests

Subjects will undergo pulmonary function tests (spirometry) according to American Thoracic Society and European Respiratory Society recommendations in the clinic.

The FEV₁ values will be recorded in the CRF.

3.5.5.6 Hypoglycemic Events

A hypoglycemic episode is defined as any event with SMBG <70 mg/dL (i.e., Level 1 hypoglycemia) or SMBG <54 mg/dL (i.e., Level 2 hypoglycemia). Severe hypoglycemic events are defined as events requiring assistance of another person to actively administer carbohydrate, glucagon, or other resuscitative actions. Severe hypoglycemic events will be documented as SAEs in the CRF. Nonsevere hypoglycemic events will not be documented as AEs but will be recorded in the hypoglycemia page of the CRF.

After the standardized meal challenges at Visit 2 and Visit 3, subjects will be monitored for signs of hypoglycemia. Subjects exhibiting signs of hypoglycemia will be treated as appropriate (e.g., provided with a snack or glucose) and the type of treatment given and time will be recorded. If a subject experiences hypoglycemia, SMBG measurements should be performed every 15 minutes until hypoglycemia is resolved.

3.5.5.7 Clinical Laboratory Tests

The clinical site will collect blood samples for HbA1c from subjects at Visit 1 and samples will be forwarded to the central laboratory for analysis. Urine pregnancy tests (for β -human chorionic gonadotropin) will be performed locally for women of child-bearing potential only.

3.5.5.8 Adverse Events

All AEs occurring after enrollment and through the duration of the study will be recorded. See Section 4 for additional information.

3.5.6 Appropriateness of Measurements

All assessments to be used in this study are commonly used and generally recognized as relevant in diabetes studies.

4 ADVERSE EVENT REPORTING

Throughout the course of the study, all AEs will be monitored and recorded in an AE page of the CRF, including the AE's description, start and end date, seriousness, severity, action taken, and relationship to the study drug. If AEs occur, the first concern will be the safety of the study subjects. All AEs will be followed until resolved or stable and the outcome documented in the CRF.

4.1 Definitions and Criteria

4.1.1 Adverse Events

Per International Council for Harmonisation of Technical Requirements for Pharmaceuticals for Human Use (ICH) E2A, an AE is any untoward medical occurrence in a subject or clinical investigation subject administered a pharmaceutical product and which does not necessarily have to have a causal relationship with this treatment. An AE can therefore be any unfavorable and unintended sign (including an abnormal laboratory finding, for example), symptom, or disease temporally associated with the use of a medicinal product, whether or not considered related to the medicinal product.

The intensity of each AE will be determined according to the following criteria:

- Mild: no modification of daily activities and does not require corrective/symptomatic treatment.
- Moderate: hinders normal daily activities and/or requires corrective/symptomatic treatment.
- Severe: prevents daily activities and requires corrective/symptomatic treatment.

Medical interventions such as surgeries, diagnostic procedures, and therapeutic procedures are not AEs but the action taken to treat a particular medical condition. They should be recorded as treatment of the AEs.

4.1.2 Serious Adverse Events

An SAE or reaction is any untoward medical occurrence that at any dose:

- Results in death
- Is life-threatening
- Requires inpatient hospitalization or prolongation of existing hospitalization
- Results in persistent or significant disability or incapacity
- Is a congenital anomaly or birth defect
- Is an important medical event (e.g., intensive treatment in an emergency room or at home for allergic bronchospasm; blood dyscrasias, or convulsions that do not result in hospitalization; or development of drug dependency or drug abuse; malignancy tumors [histologically different from primary tumor])

Medical and scientific judgment should be exercised in deciding whether expedited reporting is appropriate in other situations, such as important medical events that may not be immediately life-threatening or result in death or hospitalization but may jeopardize the subject or may require intervention to prevent one of the other outcomes listed in the definition above.

Seriousness (not severity) serves as a guide for defining regulatory reporting obligations. An SAE is not necessarily severe (e.g., an overnight hospitalization for a diagnostic procedure must be reported as an SAE even though the occurrence is not medically serious). Furthermore, a severe AE is not necessarily serious (e.g., nausea of several hours' duration may be rated as severe but may not be considered serious).

4.1.3 Adverse Events of Special Interest

An AESI is an AE (serious or nonserious) of scientific and medical concern, specific to the investigational medicinal product or program, for which ongoing monitoring and rapid communication by the Investigator to the Sponsor may be appropriate. Such events may require further investigation in order to characterize and understand them.

For AESIs, the Sponsor must be informed immediately (i.e., within 24 hours), per the SAE notification guidelines described in Section [4.2.2](#).

The following AEs are considered AESIs:

- Acute bronchospasm
- Clinically relevant decline in pulmonary function (>20% decline from baseline percent predicted FEV₁ accompanied by respiratory symptoms)
- Hypersensitivity reactions, including anaphylaxis, which can occur with insulin products, including AfreZZa
- DKA

The following diagnostic criteria must be met to be considered a DKA event ([ADA 2004](#)):

- Arterial blood pH <7.30 or serum bicarbonate <15 mEq/L
- Blood glucose >250 mg/dL (or >13.9 mmol/L)
- Serum ketones or large/moderate urine ketones
- Symptoms such as polyuria, polydipsia, nausea, or vomiting
- Treatment provided in a health care facility

4.1.4 Abnormal Laboratory Values

Any abnormality in a laboratory value that is new in onset or that has worsened in severity or frequency from the baseline condition and meets one of the following criteria will be recorded in the AE pages of the CRF:

- Requires therapeutic intervention or diagnostic tests
- Leads to discontinuation of study drug
- Has accompanying or inducing symptoms or signs

- Is judged by the Investigator as clinically significant

4.1.5 Assessing Relationship

The Investigator will classify every AE according to its relationship to study drug, study device, or study-related procedure. The AE relationship categories that will be used are listed below:

Related:

- An AE that occurs at a reasonable time interval after administration of the investigational product, use of the device, or procedure
- An AE that follows a known response pattern to the investigational product, use of the device, or procedure
- An AE that improves after stopping the investigational product, use of the device, or procedure and reappears after repeated exposure to the investigational product, device, or procedure. Depending on the nature of the AE, rechallenge may not be possible.

Probably related:

- An AE that occurs at a reasonable time interval after administration of the investigational product, use of the device, or procedure
- An AE that follows a known response pattern to the investigational product, use of the device, or procedure, where an alternative explanation (e.g., a concomitant drug or concurrent disease) is less likely

Possibly related:

- An AE that occurs at a reasonable time interval after administration of the investigational product, use of the device, or procedure
- An AE that follows a known response pattern to the investigational product, use of the device, or procedure, but could have been produced by the subject's clinical status or by other therapies

Unlikely related:

- An AE for which sufficient information exists to indicate that the etiology is unrelated to the investigational product, use of the device, or procedure
- An AE for which another etiology is specified

Not related:

- An AE without a temporal relationship to the investigational product (e.g., an AE occurring in a subject who has not received investigational product), use of the device, or procedure
- An AE for which another cause is known

4.2 Reporting Procedures and Requirements

4.2.1 Adverse Events

Any AEs occurring from when the subject enrolls in the study (consent date) until they exit the study will be recorded.

The Investigator should document all AEs in the subjects' source documentation, on the AE page of the CRF, and the SAE report (if the AE is serious). AEs of hypoglycemia that meet SAE criteria should be documented in the AE page of the CRF and SAE report.

The Investigator should specify the date of the onset of the AE, the intensity (see definitions in Section 4.1), action taken with respect to the study drug, corrective treatment/therapy given, additional investigations performed, outcome, and the relationship to study drug (Section 4.1.5). Whenever possible, the diagnosis or syndrome should be reported instead of individual associated symptoms (e.g., record "influenza" if this is the diagnosis instead of "fever" and "chills").

Every AE and SAE should be followed until resolved, or resolved with sequelae, or considered stable in the opinion of the Investigator. To the extent possible, event resolution information will be obtained by means of due diligence (see the site operations manual).

If the severity of an AE increases, a new AE page in the CRF must be completed for that AE. The date of change would be included as the end date for the original AE and the start date for the new AE of greater severity.

4.2.2 Adverse Events of Special Interest and Severe Hypoglycemia

As soon as possible (desired within 24 hours of Investigator or study coordinator awareness), the investigational center staff must report all events of severe hypoglycemia and AESIs (including DKA) to the Sponsor. For these events, the AE page of the CRF will be completed with all known details as soon as possible, this will serve as notification to the Sponsor. If the study database cannot be accessed due to technical problems, contact the Sponsor and provide the known details of the event. Once the access issue has been corrected, the event should be entered onto an AE page in the CRF.

Source documents that support the event (e.g., clinic notes, hospital admission and discharge records, lab reports, emergency medical technician reports, emergency room/urgent care) should be provided to the Sponsor. All source documents/medical records should be redacted. Each source page should be identified with the subject identification number.

4.2.3 Serious Adverse Events

Prompt notification by the Investigator to the Sponsor of an SAE (within 24 hours) is essential so that legal obligations and ethical responsibilities toward the safety of participants and the safety of a study intervention under clinical investigation are met.

The Sponsor has a legal responsibility to notify both the local regulatory authority and other regulatory agencies about the safety of a study intervention under clinical investigation. The Sponsor will comply with all applicable regulatory requirements relating to safety reporting to the regulatory authority, institutional review board (IRB), and investigators.

Any SAE brought to the attention of the Investigator at any time after the end of the study for the subject and considered by the Investigator to be caused by the investigational product with a reasonable possibility should also be reported.

4.3 Procedures for Documenting Pregnancy During Study

If a female subject becomes pregnant during the study, the Investigator will notify the medical monitor immediately following pregnancy confirmation. A subject who becomes pregnant over the course of this study will be discontinued from study drug and followed for safety outcomes until 30 days beyond resolution of the pregnancy. Pregnancy is not in and of itself an AE. However, if any adverse findings in a child or fetus of a subject exposed to the study drug before conception or during pregnancy should be reported as AEs.

5 DATA MANAGEMENT AND STATISTICAL ANALYSIS

5.1 Data Management Considerations

Paper CRFs will be employed for this study. Completed CRFs for this study will be forwarded to the Sponsor or its representative where editing and construction of a validated database will occur. Data will be quality checked, double-entered, and verified before entry into the database. Queries will be issued for any inconsistencies, omissions, and discrepancies and will be resolved by the appropriate parties. The statistical analysis of these data will be performed by the Sponsor or its representative. All AEs will be coded using the latest version of the Medical Dictionary for Regulated Activities (MedDRA). Concomitant medications will be coded using the latest version of WHODrug Global. Data management details will be outlined in a separate data management plan.

5.2 Statistical Considerations

Any deviations from the analyses described below will be documented prior to database lock, which will be described in the clinical study report.

5.2.1 General Considerations

All statistical processing will be performed using the most current version of SAS® software (SAS Institute Inc, Cary, NC) at the time of the analysis. Summary tables (descriptive statistics and/or frequency tables) will be provided for screening and/or baseline variables, efficacy variables, and safety variables. Continuous variables will be described by descriptive statistics (n, mean, median, standard deviation, minimum, and maximum). Frequency counts and percentage of subjects within each category will be provided for categorical data.

Individual data will be listed and sorted by treatment, subject identification number, visit, and time point.

Database lock will occur upon the completion of the study.

5.2.2 Randomization

This study is an open-label, single-arm study (not randomized).

5.2.3 Sample Size Justification

The sample size (20 subjects completing the study) was not determined using statistical methods, but rather was chosen based on clinical considerations.

5.2.4 Analysis Populations

All subjects in the clinical study who receive a dose of AfreZZa will be included in the analyses reported at the end of the study.

5.2.5 Protocol Deviations

Major protocol deviations (number and percentage of subjects) will be summarized. All protocol deviations will be reviewed by clinical and statistical personnel to identify important deviations

(those anticipated to have an impact on efficacy or safety findings) before the primary database lock.

5.2.6 Subject Disposition

Disposition (the number and percentage of subjects completed or discontinued from the study) will be summarized by visit and/or study period. Reasons for discontinuation will also be summarized.

5.2.7 Demographic and Baseline Characteristics

Demographic and baseline characteristics, including usual basal and bolus insulin doses, at screening will be summarized descriptively. Summary statistics will include frequency and percentage, means, standard deviation, minimum, and maximum as appropriate.

5.2.8 Medical History

Medical history data will be collected at the screening visit. The number and percentage of subjects with each medical history preferred term and system organ class will be summarized.

5.2.9 Concomitant Medications

All nonstudy medications will be coded with the current version of WHO Drug Global. Concomitant medications refer to nonstudy medications that have been used on or after administering the first dose of study drug. Among the concomitant medications, new concomitant medications refer to medications that are started after administering the first dose of study drug.

The number and percentage of subjects administering concomitant medications and new concomitant medications will be summarized by Anatomic Therapeutic Chemical Classification System Level 4 category and preferred term.

5.2.10 Treatment Exposure and Compliance

Descriptive statistics will be used to summarize subject dosing information including the basal, bolus, and total insulin doses by visit.

A by-subject listing of study drug administration will also be provided.

5.2.11 Efficacy Analyses

SMBG values will be summarized by visit. A summary table with descriptive statistics (n, mean, median, standard deviation, minimum, and maximum) by time point relative to AfreZZA dosing will be provided. SMBG data will also be presented graphically.

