Test Product, Dose, and Mode of Administration:	
Test product: AfreZZa® [insulin human] inhalation powder
 
Active ingredient: Human insulin, recombinant DNA origin
 
Dose regimen: Individualized
 
Mode of Administration: Oral inhalation

Basal Insulin Therapy Dose, and Mode of Administration:	
Basal insulin analog: The subject's personal basal insulin. The dose and type of basal insulin should not be changed between Visits 1 and 3.
 
Dose regimen: Individualized
 
Mode of Administration: Subcutaneous injection or via pump. Note: Pumps cannot be in automated insulin delivery mode for the 3 hours before or during Visits 2 and 3.

Duration of Treatment:	Two individual doses of AfreZZa will be administered during this study, during Visits 2 and 3, with a standardized meal challenge.
Criteria for Evaluation:	
This study will evaluate the efficacy and safety of AfreZZa administered according to new dosing guidelines, combined with basal insulin, based on the endpoints outlined below:
 
Efficacy Endpoint
 
 Change in SMBG from immediately before administering the dose of AfreZZa (t=0; baseline) to 15, 30, 45, 60, 90 and 120 minutes after AfreZZa dosing 
Safety Endpoints
 
 Event rates and incidence Level 1 (<70 mg/dL) and Level 2 (<54 mg/dL) hypoglycemic events Event rates and incidence of severe hypoglycemic events, defined as events requiring assistance of another person to actively administer carbohydrate, glucagon, or other resuscitative actions Incidence and severity of AEs: TEAEs, SAEs, and AESIs Change in FEV₁ from t=0 to 120 minutes after AfreZZa dosing
Statistical Methods:	
Sample Size Determination
 
Twenty subjects are planned to complete the study. Subjects who do not complete the study may be replaced. The sample size of 20 subjects was not determined using statistical methods, but rather was chosen based on clinical considerations.
 
Analysis Populations

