	
All subjects in the clinical study who receive a dose of AfreZZa will be included in analyses.
 
Analysis of Efficacy Endpoints
 
SMBG values will be summarized by visit. A summary table with descriptive statistics (n, mean, median, standard deviation, minimum, and maximum) by time point relative to AfreZZa dosing will be provided. SMBG data will also be presented graphically.
 
Analysis of Safety Endpoints
 
The incidence of hypoglycemia (total, nocturnal, and severe) and number of hypoglycemic episodes will be summarized. Summary tables providing frequency counts and the percentage of subjects within each category will be provided for Level 1 hypoglycemia (SMBG <70 mg/dL) and Level 2 hypoglycemia (SMBG <54 mg/dL). Exposure-adjusted incidence rates and exposure-adjusted event rates will be calculated and summarized. The number and percentage of subjects with TEAEs will be tabulated by system organ class and preferred term by relationship to treatment and by severity.
 
A summary table by study visit with descriptive statistics for FEV₁ at all time points will be provided. The FEV₁ data will also be presented graphically.

--	---

TABLE OF CONTENTS

SIGNATURE PAGE	2
SYNOPSIS.....	3
TABLE OF CONTENTS.....	9
TABLES	11
LIST OF ABBREVIATIONS AND DEFINITIONS OF TERMS.....	12
1 INTRODUCTION	14
1.1 Background	14
1.2 Study Rationale.....	14
1.3 Risks and Benefits.....	15
2 STUDY OBJECTIVES.....	16
2.1 Primary Objective	16
2.2 Secondary Objective	16
3 INVESTIGATIONAL PLAN.....	17
3.1 Overall Study Design and Plan	17
3.2 Study Duration.....	17
3.3 Selection of Study Population.....	17
3.3.1 Inclusion Criteria	18
3.3.2 Exclusion Criteria	18
3.3.3 Removal of Subjects from Therapy or Assessment.....	19
3.3.4 Replacement of Subjects.....	20
3.4 Treatments.....	20
3.4.1 Details of Study Treatments and Storage Conditions	20
3.4.2 Dosage Schedule	21
3.4.3 Treatment Assignment.....	21
3.4.4 Drug Packaging and Blinding.....	22
3.4.5 Drug Inventory and Accountability	22
3.4.6 Treatment Compliance.....	22
3.4.7 Prior and Concomitant Illnesses and Treatments.....	22
3.5 Assessments	23
3.5.1 Schedule of Assessments	23

3.5.2	Study Procedures	25
3.5.3	Procedures for Subjects Who Prematurely Withdraw from the Study	30
3.5.4	Efficacy Assessment	30
3.5.5	Safety Assessments	30
3.5.6	Appropriateness of Measurements.....	32
4	ADVERSE EVENT REPORTING.....	33
4.1	Definitions and Criteria.....	33
4.1.1	Adverse Events	33
4.1.2	Serious Adverse Events	33

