1.2 Study Rationale

The current study aims to evaluate 2 different doses of Afrezza in adults ≥ 18 years of age. Subjects will administer an Afrezza dose based on the current prescribing information (PI) with a meal challenge, and then proceed to a second meal challenge where a second Afrezza dose will be administered based on the subject's RAA dose multiplied by 2 and rounded down to the nearest Afrezza cartridge size, subject to Investigator discretion.

Pooled Afrezza trial data suggests that subjects achieve similar glycemic control with a dose ratio of 1.5- to 2-fold the equivalent unit value of a SC insulin analog in head-to-head comparisons (Kendall et al. 2020, Grant et al. 2019). Thus, the Sponsor has chosen to evaluate 2 different doses of Afrezza to assess whether a higher dose results in improved postprandial glucose control.

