2 STUDY OBJECTIVES

2.1 Primary Objective

The primary objective of this study is:

- To evaluate the efficacy of Afrezza administered at 2 different doses, combined with basal insulin, in adults 18 years and older with T1DM or T2DM as measured by:
 - Mean change from baseline in postprandial glucose based on self-monitored blood glucose (SMBG) from immediately before administering the dose of Afrezza (t=0; baseline) to 15, 30, 45, 60, 90 and 120 minutes after Afrezza dosing in conjunction with a standardized meal challenge

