3 INVESTIGATIONAL PLAN

3.1 Overall Study Design and Plan

MKC-TI-191 is a Phase 4, single-arm, multicenter clinical trial evaluating the efficacy and safety of Afrezza, administered according to the current Afrezza PI compared to a titrated dose, in combination with a basal insulin in adult subjects (≥ 18 years of age) with T1DM or T2DM.

Eligible subjects will be on a stable regimen consisting of a basal-bolus insulin therapy prior to screening.

The study is composed of up to 4 clinic visits (screening, 2 treatment visits, and a follow-up visit):

- **Screening (Visit 1):** Informed consent will be obtained and eligibility confirmed. Eligible subjects will be enrolled at Visit 1.
- **Visit 2:** The first dose of Afrezza will be based on the dose of SC RAA that the subject would normally take, converted according to the guidelines provided in the current Afrezza PI. If the subject's normal RAA dose is <4 units, the subject will be asked to consume enough nutritional shake, per their normal insulin:carbohydrate ratio, to cover an RAA dose of ≥ 4 units such that their Afrezza dose at Visit 3 is higher than the dose taken at Visit 2. After completing the standardized meal challenge, the Investigator will decide, based on the subject's glucose excursion at Visit 2, if the subject should proceed to Visit 3 where a second dose of Afrezza will be administered.
- **Visit 3:** The second dose of Afrezza will be based on the dose of SC RAA that the subject would normally take, converted by multiplying their RAA dose by 2 and rounding down to the nearest Afrezza cartridge size.
- **Follow-up Visit (Visit 4):** Subjects will return for safety assessments, including a final FEV₁ measurement, 24 to 72 hours after their last dose of Afrezza.

See Section 3.5 for information on the assessments to be performed at these visits.

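### The efficacy analysis text tabulates SMBG values by visit; it names neither change from each visit's t=0 (the primary measure) nor a within-subject Visit 3 minus Visit 2 summary

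*Combined protocol and SAP*

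**What the plan says.** Section 5.2.11 plans: "SMBG values will be summarized by visit. A summary table with descriptive statistics (n, mean, median, standard deviation, minimum, and maximum) by time point", together with graphs. The Synopsis repeats this under Analysis of Efficacy Endpoints, beginning "SMBG values will be summarized by visit". Neither place mentions change from the pre-dose reading, a between-visit difference or a confidence interval.

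Other sections define what is to be learned:

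- Section 2.1 and the Synopsis (Criteria for Evaluation) make the efficacy measure the change in SMBG from t=0 to 15, 30, 45, 60, 90 and 120 minutes. Section 3.5.2.2 makes each visit's t=0 reading the baseline for that visit and allows it to lie between 100 and 200 mg/dL.
- Section 1.2 says two doses are studied "to assess whether a higher dose results in improved postprandial glucose control". Section 3.1 describes Afrezza "administered according to the current Afrezza PI compared to a titrated dose".
- Section 3.1 lets the investigator decide on progression to Visit 3 from the Visit 2 glucose excursion. Section 5.2.4 analyses everyone who receives a dose.
- Section 5.2.1 adds two general promises: "Summary tables (descriptive statistics and/or frequency tables) will be provided for screening and/or baseline variables, efficacy variables, and safety variables", and "Individual data will be listed and sorted by treatment, subject identification number, visit, and time point".

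**The concern.** The analysis text describes a different quantity from the endpoint and stops short of the comparison the study was set up to make. Two design features make raw-value columns hard to read as a dose comparison.

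First, starting glucose can differ between visits by chance, and a table of values carries that difference into the later time points.

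Second, the Visit 2 column holds all dosed subjects, while the Visit 3 column holds only those the investigator sent on. The two may be different sets, separated on the outcome itself. How many subjects will be dosed is also unclear: Section 3.3 says non-completers may be replaced and Section 3.3.4 says they will not be.

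At stake is the reading of the study's main result. By-visit SDs cannot give the precision of a within-subject difference. If the summary is not fixed in advance, the headline comparison (values or changes, all dosed or paired) can be chosen after open-label data have been seen.

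**Working it through.** **No planned figure to reproduce.** Section 5.2.3 says the 20 completers were not derived statistically, and no SD, effect size or correlation is stated. Every SD and correlation below is an assumption.

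**1. What the named table can and cannot supply**

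| Quantity | Named in 5.2.11? | Recoverable from the named table? |
|---|---|---|
| Mean SMBG by visit and time | Yes | Yes |
| Mean change from t=0 | No | Yes, if the same subjects have both readings |
| SD, median and range of change | No | No |
| Mean paired Visit 3 minus Visit 2 difference | No | Only if the same subjects attend both visits |
| SD of that difference | No | No |

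Section 5.2.1 may be read to cover the change rows. Nothing in Section 5.2 covers the last two.

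**2. Chance difference in starting glucose.** For the same 20 subjects, SE = SD0 × √(2(1−r)) / √20. The upper SD0 is a uniform spread over the permitted range, 100/√12 = 28.9; the lower is 15.

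- SD0 = 15, r = 0.5: SE 3.4 mg/dL, 95% range ±6.6.
- SD0 = 28.9, r = 0: SE 9.1 mg/dL, 95% range ±17.9.

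Raw values carry this into the visit comparison to the extent that starting glucose persists. If it persists fully and the Visit 3 baseline is 20 mg/dL higher, a −30 difference in change appears as −30 + 20 = −10 in values.

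**3. Different subjects in the columns (invented example).** Suppose 16 of 20 proceed and go from +60 to +30, while the 4 who do not proceed averaged −10 at Visit 2. The Visit 2 mean is (16×60 + 4×(−10))/20 = 46. The columns differ by 30 − 46 = −16; the within-subject difference is −30.

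**4. Precision.** The paired 95% half-width is t(0.975, n−1)/√n × SD of the difference: a multiplier of 0.468 at n = 20 and 0.554 at n = 15. With SD of change 40 at each visit, the SD of the difference is 40√(2(1−r)). Treating the columns as independent gives t(0.975, 38) × 40 × √(2/20) = 25.6.

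| r | SD of difference | Paired half-width | 25.6 ÷ paired |
|---|---|---|---|
| 0 | 56.6 | 26.5 | 0.97 |
| 0.3 | 47.3 | 22.2 | 1.16 |
| 0.5 | 40.0 | 18.7 | 1.37 |
| 0.7 | 31.0 | 14.5 | 1.77 |

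At r = 0 pairing gains no precision.

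**5. Spread of change within a visit.** With SDs of 25 at t=0 and 40 later, SD of change = √(25² + 40² − 2r×25×40). This is 47, 35 or 21 mg/dL at r = 0, 0.5 or 0.9, so the value SDs alone do not determine it.

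**6. What pairing does not cure.** Take an assumed worst case: 25 dosed, exactly the 20 largest Visit 2 excursions proceed, no dose effect, SD 40. The selection intensity at p = 20/25 is i = φ(z)/p = 0.350. Column bias is +r×40×i; paired bias is −(1−r)×40×i.

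| r | Column bias (mg/dL) | Paired bias (mg/dL) |
|---|---|---|
| 0.3 | +4.2 | −9.8 |
| 0.5 | +7.0 | −7.0 |
| 0.7 | +9.8 | −4.2 |

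A simulation at r = 0.5 (40,000 runs) gives +6.8 and −6.7. If the investigator's decision correlates only 0.5 with the excursion, the biases halve, to +3.5 and −3.5 at r = 0.5. If everyone proceeds, both are zero.

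**The case against.** The strongest reply has four parts.

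1. The objective fixes the variable, the statistic, the times and the baseline, and Section 5.2.1 promises summaries of efficacy variables, so a change table is the natural output. This largely stands: the first half of the point is a mismatch in drafting, not an undefined endpoint.

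2. The primary objective evaluates efficacy at two doses without naming a difference, and the study is a small, non-randomised proof of concept with no hypothesis test. It stands that no error rate or sample size is affected and that descriptive reporting is suitable. But the rationale and the design statement both describe a comparison of doses, and the plan contains no summary of one.

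3. The paired difference can mislead more than the columns. Under the worst case in the working, its bias is larger in size whenever the correlation is below 0.5, and it favours the higher dose, whereas the column bias runs against it. This stands as a reason for an explicit caveat and for showing Visit 2 by who proceeds. It is not a reason to leave the comparison unspecified. The caveat should also cover carbohydrate given for hypoglycemia during the 2 hours (Section 3.5.5.6), and the meal of one to two bottles, whose amount is not stated to match across visits.

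4. A t=0 imbalance would be visible in the table, and the reported n, disposition by visit and listings would reveal unequal columns. True, but seeing a mismatch does not supply the matched summary, and pairing from listings by hand is not a pre-specified analysis. The wide independent-columns interval is a reader's likely calculation, not one the plan proposes, and its error is conservative for correlations of 0.3 or more.

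**Conclusion.** The point holds and should be fixed. The weightier half is the missing within-subject Visit 3 minus Visit 2 summary, which nothing in Section 5.2 supplies; the missing change-from-t=0 table is a smaller gap that a generous reading of Section 5.2.1 could fill.

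The case for pairing rests on matched composition and on an honest estimate of precision. The first does not depend on any assumed correlation; the second does. Pairing does not remove the effects of fixed dose order or of selection on the Visit 2 excursion. Confidence is high about what the text omits. The mg/dL figures only illustrate the scale, because the documents give no SDs or correlations.

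**What to change.** In Section 5.2.11 and its Synopsis copy:

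1. Tabulate change from that visit's t=0 SMBG at 15, 30, 45, 60, 90 and 120 minutes, by visit, with n, mean, SD, median, minimum and maximum. Show Visit 2 for all dosed subjects, and separately for those who do and do not proceed to Visit 3.
2. In subjects with both visits, report the paired Visit 3 minus Visit 2 difference in change at each time, with a 95% confidence interval labelled as descriptive.
3. State beside that result that fixed dose order and investigator selection on the Visit 2 excursion can bias it, and that if larger excursions are the ones that proceed, regression to the mean favours the higher dose. Mention rescue carbohydrate and any difference in shake amount between visits.

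The cost is wording and a few extra tables. The readings are already scheduled, the individual data will already be listed, and Section 5.2 allows analysis changes to be documented before database lock. The downside is that intervals from about 20 subjects could be over-read, which is why the caveat belongs in the plan.
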